After treatment discontinuation, each subject will be followed for 30 days for AE monitoring. Subjects will be monitored for SAEs for 90 days after treatment discontinuation, 30 days if the subject initiates new anticancer therapy less than 30 days after study treatment discontinuation, or the day new anticancer therapy is initiated if between 30 days and 90 days after study treatment discontinuation. Subjects with an ongoing AE of Grade >1 at the time of treatment discontinuation will be followed until resolution of the AE to Grade 0 to 1, until considered stable by the treating physician, or until beginning a new anticancer therapy, whichever occurs first.

Subjects who discontinue treatment for reasons other than confirmed disease progression will have posttreatment follow up for disease status until disease progression, initiating a new anticancer therapy, withdrawing consent for study participation, or becoming lost to follow up.

After confirmed disease progression each subject will be contacted by telephone approximately every 12 weeks (84 \pm 7 days) for survival until withdrawal of consent to participate in the study, becoming lost to follow up, death, or end of the study, whichever occurs first.

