7.1.2.6 Disease Assessments

Response will be based on RECIST 1.1 (Appendix 12.4) as assessed by investigator/local radiology review. Images used for tumor measurements will be sent to a central imaging vendor for potential blinded, central review. The process for image collection and transmission to the central imaging vendor can be found in the SIM.

Immunotherapeutic agents, such as pembrolizumab, may produce antitumor effects by potentiating an endogenous cancer-specific immune response. The response patterns seen with such an approach may extend beyond the usual time course of responses seen with typical cytotoxic agents, and can manifest a clinical response after an initial increase in tumor burden or even the appearance of new lesions. Subjects could, at the discretion of the investigator, continue in the trial until the initial assessment of progressive disease is confirmed at least 4 weeks later (refer to Section 4.2.3.1). The details on the irRECIST assessment can be found in Appendix 12.5.

Initial imaging (eg, CT scan, MRI, positron emission tomography) should be performed within 28 days prior to the first dose of study treatment, and should be repeated 9 weeks after the first dose and every 9 weeks until confirmed progressive disease, initiating a new anticancer therapy, withdrawing consent for study participation, or becoming lost to follow up, whichever occurs first.

The same imaging technique should be used at each time point and the schedule of disease assessment should not be adjusted for delays, if any, in cycle starts.

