7.1.5.5 Survival Status

To ensure current and complete survival data are available, updated survival status may be requested during the course of the study by the Sponsor. Upon Sponsor notification, all subjects who do not/will not have a scheduled study visit or study contact during the Sponsor-defined time period will be contacted for their survival status (excluding subjects who have a previously recorded death event in the collection tool).

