8.4 Analysis Endpoints

8.4.1 Efficacy/Immunogenicity/Pharmacokinetic Endpoints

Efficacy endpoints are secondary and exploratory endpoints in this study (refer to Sections 3.2 and 3.3).

The following efficacy endpoints are derived from the RECIST 1.1 criteria:

Objective Response Rate: defined as the proportion of subjects who have achieved confirmed CR or PR.

Duration of Response: defined for subjects who achieved a tumor response (CR or PR) as the time between the date of the first documented tumor response and the subsequent date of the objectively documented disease progression or death, whichever occurs first. Response duration for subjects who have not progressed or died at the time of analysis will be censored at the date of their last tumor assessment.

Disease Control Rate: defined as the proportion of subjects who have achieved CR, PR, or SD.

Progression-free Survival: defined as the time from the first dose of study medication to the first objective documentation of tumor progression or death due to any cause. Detailed censoring rules will be described in the sSAP.

Overall survival: defined as the time from the first dose of study medication to death due to any cause. Subjects who did not die will be censored on the date of their last study assessment or contact.

PK endpoints include serum concentrations of MK-8353 and pembrolizumab and derived PK parameters.

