- New lesion resulting in initial progressive disease is qualitatively worse
- Additional new lesion(s) since last evaluation
- Additional new non-target progression since last evaluation

ALL of the following conditions must be met in order for progressive disease NOT to be confirmed at repeat imaging:

- Tumor burden is $< 20\%$ or < 5 mm absolute increase compared to nadir
- Non-target disease resulting in initial progressive disease is stable or qualitatively improved
- New lesion resulting in initial progressive disease is stable or qualitatively improved
- No incremental new lesion(s) since last evaluation
- No incremental new non-target progression since last evaluation

Additional details about irRECIST are referenced in the Merck TIP Sheet for RECIST 1.1 and irRECIST.

When feasible, subjects should not be discontinued until progression is confirmed by the local site investigator/radiology assessment.

Table 13 Imaging and Treatment after First Radiologic Evidence of Progressive Disease for Subjects Receiving Pembrolizumab (MK-3475) (management per irRECIST)

	Clinically Stable		Clinically Unstable	
	Imaging	Treatment	Imaging	Treatment
1st radiologic evidence of PD by RECIST 1.1 ⁽¹⁾	Repeat imaging at \geq 4 weeks at site to confirm PD	May continue study treatment at the investigator's discretion while awaiting confirmatory tumor imaging.	Repeat imaging at \geq 4 weeks to confirm PD per physician discretion only	Discontinue treatment
Repeat tumor imaging confirms PD by irRECIST at the local site	No additional imaging required	Discontinue treatment ⁽²⁾	No additional imaging required	N/A
Repeat tumor imaging shows SD, PR or CR by irRECIST by the local site	Continue regularly scheduled imaging assessments	Continue study treatment at the local investigator's discretion	Continue regularly scheduled imaging assessments	May restart study treatment if condition has improved and/or clinically stable per investigator's discretion. Next tumor image should occur according to the regular imaging schedule outlined in the protocol

1) Disease progression will be assessed by the local site/investigator for subjects participating in the study. All images will be submitted to a central imaging vendor for potential analysis at the end of the study.

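### Routine survival calls are triggered by confirmed progression, which some subjects need never reach, so exploratory OS is at risk of informative censoring unless an optional Sponsor request fills the gap

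*Combined protocol and SAP*

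**What the plan says.** **When survival calls start.** Section 5.8.1: "After confirmed disease progression each subject will be contacted by telephone approximately every 12 weeks". Sections 2.1, 5.8.1.1 and 7.1.5.4 and note 12 of both flow charts use the same trigger. The column that note 12 annotates, however, is headed as 12-weekly from discontinuation and says nothing of progression.

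**When the preceding phase ends.** Under Section 5.8.1, subjects who stop treatment without confirmed progression "will have posttreatment follow up for disease status until disease progression, initiating a new anticancer therapy", or until withdrawal of consent or loss to follow-up. Progression here is not qualified as confirmed. Section 7.1.2.6 does qualify it, and runs imaging "every 9 weeks until confirmed progressive disease, initiating a new anticancer therapy, withdrawing consent for study participation, or becoming lost to follow up".

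**When confirmation is not required.** In Table 13 (Appendix 12.5), a clinically unstable subject with first radiologic progression stops treatment, and repeat imaging is "to confirm PD per physician discretion only". Section 5.8.1 lists clinical progression as a stopping reason separate from confirmed radiological progression.

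**Censoring and the safeguard.** Section 8.4.1: "Subjects who did not die will be censored on the date of their last study assessment or contact". Section 7.1.5.5: "To ensure current and complete survival data are available, updated survival status may be requested during the course of the study by the Sponsor". Once the Sponsor asks, every subject without a scheduled visit or contact is to be contacted, apart from recorded deaths.

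**The concern.** A subject handled exactly as written can leave disease-status follow-up without ever meeting the trigger for survival calls. Three routes lead there: clinically unstable at first progression with no repeat scan, stopping for clinical progression alone, and starting new therapy before confirmation. The last guaranteed contact may then be the 30-day or 90-day safety visit.

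SAE reporting is not a dependable substitute. Its window closes at 90 days at the latest, and progression of the cancer under study is excepted from it (Section 7.2.3.3).

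If the subjects lost in this way have a different prognosis from those followed, censoring is informative. There is no concurrent control to share the error. Because the text and the flow chart give different triggers, sites may also follow subjects differently. Deaths not collected at the time may be hard to recover later.

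**Working it through.** The documents give no OS median, event count or power, so there is no stated figure to reproduce. The check has two parts.

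**1. The passages side by side**

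| Subject | Disease-status follow-up ends | Is the survival-call trigger met? |
|---|---|---|
| Progression confirmed on repeat scan | At confirmation | Yes |
| Clinically unstable at first progression, no repeat scan | At progression, if 5.8.1 is read literally | No |
| Stops for clinical progression only | At progression or new therapy | Not unless a later scan confirms |
| Starts new therapy before confirmation | At new therapy (5.8.1 and 7.1.2.6) | Not by any scheduled imaging |

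Under the flow-chart column heading, all four rows would be called. Under note 12 to that column, only the first is sure to be.

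**2. Possible size, on assumed inputs**

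None of these inputs is in the documents:
- Time to stopping A is exponential with median 3 months, rate ln 2/3 = 0.231 per month.
- Survival after stopping B is exponential, with median 9 months if confirmed (rate ln 2/9 = 0.077) and 4 months if unconfirmed (rate ln 2/4 = 0.173).
- OS time is T = A + B, with a data cut at 24 months.
- Unconfirmed subjects not reached later are censored at A + 3 months (the 90-day visit).
- Kaplan-Meier on min(T, censoring time) is compared with Kaplan-Meier under full follow-up, in a large simulated sample. The SAP leaves OS methods to the supplemental SAP, so Kaplan-Meier is also an assumption.

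| Unconfirmed | Their median after stopping | Recovered by Sponsor request | Median OS, full follow-up | Median OS, with gap | Difference |
|---|---|---|---|---|---|
| 10% | 4 months | none | 13.0 | 13.5 | +0.5 |
| 30% | 4 months | none | 11.7 | 13.0 | +1.3 |
| 50% | 4 months | none | 10.6 | 12.5 | +1.9 |
| 30% | 4 months | half | 11.7 | 12.2 to 12.3 | about +0.5 |
| 30% | 12 months | none | 14.5 | 14.4 | about 0 |
| any | any | all | as full follow-up | same | 0 |

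Twelve-month OS is about 54% against 49% in the 30% row, and about 52% against 44% in the 50% row. If the last contact is the 30-day visit, the 30% case gives a median of 14.0 months, a difference of 14.0 − 11.7 = 2.3.

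A second set of assumptions gives the same pattern: median 2 months to progression, 6 months after it if confirmed, and unconfirmed subjects censored 1 month after progression.
- 20% unconfirmed, hazard ratio 2 against confirmed subjects: 9.2 against 8.4 months (+0.8), or 8.7 months if half are recovered.
- 40%, hazard ratio 3: 8.8 against 6.9 months (+1.9).
- 20%, hazard ratio 1: 9.42 against 9.16 months (+0.26). A small excess remains at equal prognosis because, in this model, the hazard of death is higher after progression than before it, and censoring falls after progression.
- 20%, hazard ratio 0.7: 9.5 against 9.6 months (−0.1).

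**The case against.** The strongest reply is that the protocol already provides for these subjects. Section 7.1.5.5 states that its purpose is complete survival data, and its contact does not depend on confirmed progression. A later contact moves the censoring date under Section 8.4.1. Section 5.8.1 keeps subjects who stop treatment in the trial according to the flow chart, which runs a survival-status arrow across the study and times the 12-weekly column from discontinuation. Section 7.1.2.6 continues imaging until confirmed progression, and Appendix 12.5 asks sites, where feasible, not to discontinue subjects before confirmation. Both limit the unconfirmed share.

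Much of this stands. A reader might infer that these subjects are bound to be censored early and that OS is therefore biased upward. The documents do not support that, because a complete survival update would remove the problem. A reader might also infer that everyone in the gap is among the sickest. That is plausible for clinically unstable subjects, but the documents give no prognosis for those starting new therapy, and subjects fit for another line may do better.

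Materiality is also limited. OS is exploratory (Sections 3.3 and 4.2.3.1) and Section 8.7 rules out formal hypothesis testing. With 40 subjects and 12-month OS near 49%, the 95% half-width is about 1.96 × √(0.49 × 0.51/40) = 0.155, or 15 points. The shift of about 5 points in the 30% case lies inside that, although it is systematic and would not shrink with more subjects.

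The reply does not close the gap. The Sponsor request is permitted, not required, has no schedule and is not tied to an OS analysis. The flow-chart column is contradicted by its own note, and imaging under Section 7.1.2.6 still stops at new therapy.

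**Conclusion.** The point holds as a gap and an internal inconsistency, with a risk of bias and not a demonstrated one. The trigger for routine survival calls conflicts with the flow-chart column, and survival status for subjects without confirmed progression depends on an optional request.

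The direction is upward if those subjects are mainly the clinically unstable ones. The effect is small if they do about as well as the others, and nil or slightly reversed if they do better. It is zero if the survival update is complete. In the illustration the excess in median OS runs from nothing to about 2 months, but the unconfirmed share, the prognosis and the recovery rate are all assumed.

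Severity is minor to moderate: OS is an exploratory endpoint in a non-comparative Phase 1b trial, and no decision rule in the plan uses it.

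**What to change.** - In Sections 2.1, 5.8.1, 5.8.1.1 and 7.1.5.4 and in note 12 of both flow charts, start the 12-weekly survival calls when disease-status follow-up ends for any reason other than death or withdrawal of consent. This covers first or confirmed progression, clinical progression and new anticancer therapy. Word the trigger and the flow-chart column heading to match.
- Reconcile Section 5.8.1 with Section 7.1.2.6 on whether disease-status follow-up ends at first or at confirmed progression.
- In Section 7.1.5.5, require a survival-status update before each OS analysis, in addition to the present option to request one.

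The cost is a wording amendment and some extra telephone calls. Treatment, imaging and sample size are unchanged.

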5.8.1.1 Discontinuation of Trial Treatment After Disease Response

Subjects who attain an investigator-determined confirmed disease response of complete response (CR) may discontinue study treatment (MK-8353 and pembrolizumab) after receiving at least 2 additional cycles of MK-8353 and pembrolizumab, as applicable, beyond the date when the initial response was declared and after a total of at least 8 cycles of MK-8353 and pembrolizumab, as applicable. The decision to continue or discontinue study treatment after confirmed disease response is at the investigator's discretion.

After treatment discontinuation, each subject will be followed for 30 days for AE monitoring. Subjects will be monitored for SAEs for 90 days after treatment discontinuation, 30 days if the subject initiates new anticancer therapy less than 30 days after study treatment discontinuation, or the day new anticancer therapy is initiated if between 30 days and 90 days after study treatment discontinuation. Subjects with an ongoing AE of Grade >1 at the time of treatment discontinuation will be followed until resolution of the AE to Grade 0 to 1, until considered stable by the treating physician, or until beginning a new anticancer therapy, whichever occurs first.

Subjects will have posttreatment follow up for disease status until disease progression, initiating a new anticancer therapy, withdrawing consent for study participation, or becoming lost to follow up.

After confirmed disease progression each subject will be contacted by telephone approximately every 12 weeks (84 \pm 7 days) for survival until withdrawal of consent to participate in the study, becoming lost to follow up, death, or end of the study, whichever occurs first.

Subjects who discontinue study treatment after confirmed CR may be eligible to be re-treated with study treatment at the discretion of the investigator, if all of the following conditions are met:

- The subject experiences investigator-determined confirmed disease progression;
- No other anticancer therapy was administered since the last dose of study treatment;
- The subject meets the safety parameters listed in the Inclusion/Exclusion criteria; and
- The study is ongoing.

Subjects will resume study treatment in the same Part of the study and at the same dose of MK-8353 to which they were initially allocated and at the 200 mg fixed dose of pembrolizumab. The criteria for withdrawal and discontinuation after re-treatment are as

outlined in Section 5.8. Response or progression after re-treatment will not be counted toward the secondary and exploratory efficacy endpoints, ORR, or PFS of this study.

For subjects who are discontinued from treatment but continue to be monitored in the trial, see Section 6.0 and Section 7.1.5.4 for those procedures to be completed at each specified visit.

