Although there will not be any formal hypothesis testing in this study, an interim look at the data may be conducted to enable future trial planning and dosing decisions. In Part 2, a futility check will be performed after the first ~18 evaluable subjects in each cohort are enrolled. If no responses are observed, the trial may be stopped early.

Subjects will be monitored carefully for the development of adverse events (AEs), and for clinical and/or radiographic evidence of disease progression according to RECIST 1.1; however immune-related RECIST (irRECIST) could be used by the investigator for treatment decision. In subjects who have initial evidence of radiological progressive disease by RECIST 1.1, it will be at the discretion of the investigator whether or not to continue a subject on study treatment until repeat imaging is obtained. This clinical judgment decision should be based on the subject's overall clinical condition, including performance status, clinical symptoms, and laboratory data. Subjects may continue to receive study treatment until tumor assessment is repeated ≥ 4 weeks later in order to confirm progressive disease by irRECIST per site assessment.

Adverse events will be evaluated by the investigator, according to criteria outlined in the National Cancer Institute (NCI) Common Toxicity Criteria for Adverse Events (CTCAE), version 4.0, to establish the safety and tolerability of MK-8353 when administered in combination with pembrolizumab as per the primary objective of this study.

There will be no intrasubject dose escalation for subjects enrolled in this study. The definition of DLTs and criteria for dose modification of MK-8353 are outlined in Sections 5.2.1.5 and 5.2.2. Pembrolizumab will be administered at a fixed dose of 200 mg once every 3 weeks (q3w), which will not be modified.

Subjects may receive study treatment (MK-8353 and pembrolizumab) for up to 35 cycles in Arms A, B, and C (approximately 24 months) and for up to 36 cycles in Arm D. Subjects will be treated until disease progression, unacceptable toxicity, intercurrent illness that prevents further administration of treatment, investigator's decision to discontinue treatment, subject withdrawal of consent, pregnancy of the subject, subject completes treatment, or administrative reasons requiring cessation of treatment, at which point they will be discontinued from the study. Subjects will be treated thereafter at the discretion of the physician.

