5.2.1.4 Tolerability Evaluation Rules and Dose Escalation

The different dose levels of MK-8353 in Arms A and B and optional Arms C and D planned in Part 1 are presented in [Table 4](#).

In Amendment 3 of Protocol 013, the starting dose of MK-8353 is 50 mg bid in Arm A and 50 mg qd in Arm B and optional Arms C and D. Dose escalation will continue as outlined above (Section 5.2.1.2) according to mTPI dose-finding rules. Additionally, doses of MK-8353 at 10 mg and 30 mg could be explored in each arm (Section 5.2.1.2). Concomitant administration of pembrolizumab will be at the fixed dose of 200 mg q3w in all arms and at all dose levels of MK-8353.

Table 4 Dose Levels for MK-8353 + Pembrolizumab in Part 1

Arm A	MK-8353 bid continuous		Pembrolizumab (q3w)
Dose Levels	mg per dose	mg per day	IV Infusion
DL1	350	700	200
DL1A*	50	100	200
DL2A**	50 @ AM + 100 @ PM	150	200
DL3A	100	200	200
DL4A	150	300	200
DL5A	200	400	200
DL6A	300	600	200
Arm B	MK-8353 qd continuous		IV infusion
DL1B	50	50	200
DL2B	100	100	200
DL3B	150	150	200
DL4B	200	200	200
DL5B	300	300	200
DL6B	400	400	200
DL7B	600	600	200
DL8B	900	900	200
DL9B	1200	1200	200
Optional Arm C	MK-8353 qd 1 week on/1 week off		
Dose Levels	mg per dose	mg per day	IV Infusion
DL1C	50	50 for Days 1 to 7, Days 15 to 21, and Days 29 to 35 of a 42-day period (corresponding to 2 cycles of 21 days)	200
DL2C	100	100 for Days 1 to 7, Days 15 to 21, and Days 29 to 35 of a 42-day period (corresponding to 2 cycles of 21 days)	200
DL3C	150	150 for Days 1 to 7, Days 15 to 21, and Days 29 to 35 of a 42-day period (corresponding to 2 cycles of 21 days)	200
DL4C	200	200 for Days 1 to 7, Days 15 to 21, and Days 29 to 35 of a 42-day period (corresponding to 2 cycles of 21 days)	200
DL5C	300	300 for Days 1 to 7, Days 15 to 21, and Days 29 to 35 of a 42-day period (corresponding to 2 cycles of 21 days)	200
DL6C	400	400 for Days 1 to 7, Days 15 to 21, and Days 29 to 35 of a 42-day period (corresponding to 2 cycles of 21 days)	200
DL7C	600	600 for Days 1 to 7, Days 15 to 21, and Days 29 to 35 of a 42-day period (corresponding to 2 cycles of 21 days)	200

Optional Arm D	MK-8353 qd monotherapy run-in then continuous		Pembrolizumab (q3w)
Dose Levels	mg per dose	mg per day	IV Infusion
DL1D	50	50 for Cycle 1, Day 1 to Day 14 (run-in), and Day 1 to Day 21 of subsequent cycles	200
DL2D	100	100 for Cycle 1, Day 1 to Day 14 (run-in), and Day 1 to Day 21 of subsequent cycles	200

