5.2.2.1 MK-8353 Dose Modifications

Criteria for Dose Delay

Except in Cycle 1 in which dosing can be delayed up to 2 weeks, dosing of MK-8353 should be delayed for up to 3 weeks, until the AE is resolved to baseline status or \leq Grade 1 in case of:

- Any treatment-related hematological or nonhematological AE \geq Grade 3
- OR

- Any abnormal nonhematological laboratory value \geq Grade 3 that requires medical intervention, hospitalization, or persists for \geq 1 week, except for a clinically nonsignificant, treatable, or reversible laboratory abnormalities

Any \geq Grade 3 AE of nausea and/or vomiting, or anorexia if left untreated without medical intervention will not require a dose delay.

A reoccurring Grade 2 hematological or nonhematological AE, which in the opinion of the investigator is treatment-related and significant despite medical intervention, should be discussed with the Sponsor prior to any dose delay.

Subjects should be assessed weekly until the AE has resolved to baseline status or \leq Grade 1 and dosing resumes or the subject is discontinued from the study.

If treatment is delayed by more than 3 weeks (or by more than 2 weeks in Cycle 1) because of treatment-related toxicity, study treatment should be discontinued. However, subjects with evidence of clinical benefit may be allowed to continue treatment despite a treatment delay (for any reason) of more than 3 weeks, after discussion with the Sponsor.

Criteria for Dose Modification

Once a dose delay occurs, upon resolution of any treatment-related AE to baseline status or \leq Grade 1, the dose level of MK-8353 for the subsequent doses must be reduced 1 dose level.

Any dose level reduction will be permanent (ie, dose re-escalation is NOT allowed). No more than 2 dose level reductions will be allowed. Subjects who require further dose reductions or dose reductions below DL -1 should be discontinued from the study treatment.

Dose reductions are not permitted during the DLT evaluation period.

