	The following components are to be used to assess the relationship between the Sponsor's product and the AE; the greater the correlation with the components and their respective elements (in number and/or intensity), the more likely the Sponsor's product caused the adverse event (AE):	
	Exposure	Is there evidence that the subject was actually exposed to the Sponsor's product such as: reliable history, acceptable compliance assessment (pill count, diary, etc.), expected pharmacologic effect, or measurement of drug/metabolite in bodily specimen?
	Time Course	Did the AE follow in a reasonable temporal sequence from administration of the Sponsor's product? Is the time of onset of the AE compatible with a drug induced effect (applies to trials with investigational medicinal product)?
	Likely Cause	Is the AE not reasonably explained by another etiology such as underlying disease, other drug(s)/vaccine(s), or other host or environmental factors

Relationship to Sponsor's Product (continued)	The following components are to be used to assess the relationship between the test drug and the AE: (continued)	
	Dechallenge	Was the Sponsor's product discontinued or dose/exposure/frequency reduced? If yes, did the AE resolve or improve? If yes, this is a positive dechallenge. If no, this is a negative dechallenge. (Note: This criterion is not applicable if: (1) the AE resulted in death or permanent disability; (2) the AE resolved/improved despite continuation of the Sponsor's product; or (3) the trial is a single dose drug trial); or (4) Sponsor's product(s) is/are only used one time.)
	Rechallenge	Was the subject re-exposed to the Sponsor's product in this study? If yes, did the AE recur or worsen? If yes, this is a positive rechallenge. If no, this is a negative rechallenge. (Note: This criterion is not applicable if: (1) the initial AE resulted in death or permanent disability, or (2) the trial is a single dose drug trial); or (3) Sponsor's product(s) is/are used only one time). NOTE: IF A RECHALLENGE IS PLANNED FOR AN ADVERSE EVENT WHICH WAS SERIOUS AND WHICH MAY HAVE BEEN CAUSED BY THE SPONSOR'S PRODUCT, OR IF REEXPOSURE TO THE SPONSOR'S PRODUCT POSES ADDITIONAL POTENTIAL SIGNIFICANT RISK TO THE SUBJECT, THEN THE RECHALLENGE MUST BE APPROVED IN ADVANCE BY THE SPONSOR CLINICAL DIRECTOR AS PER DOSE MODIFICATION GUIDELINES IN THE PROTOCOL.

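### Re-treatment after a complete response restarts MK-8353 at the allocated dose, even for subjects whose dose was permanently reduced for toxicity

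*Combined protocol and SAP*

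**What the plan says.** Section 5.8.1.1 allows a subject with an investigator-determined, confirmed CR to stop both drugs after at least 8 cycles in total, at least 2 of them after the response was first declared. If the disease then progresses, the investigator may re-treat under four conditions: confirmed progression, no other anticancer therapy since the last dose, the entry-criteria safety parameters are met, and the study is still open. The subject then resumes in the same Part, "at the same dose of MK-8353 to which they were initially allocated", with pembrolizumab 200 mg. The paragraph continues "The criteria for withdrawal and discontinuation after re-treatment are as" set out in Section 5.8. It does not refer to the dose modification rules.

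Those rules are in Section 5.2.2.1. After a dose delay, once the treatment-related event has resolved, "the dose level of MK-8353 for the subsequent doses must be reduced 1 dose level". The section adds "Any dose level reduction will be permanent (ie, dose re-escalation is NOT allowed"), and "No more than 2 dose level reductions will be allowed". Section 2.1 states separately that "There will be no intrasubject dose escalation for subjects enrolled in this study", and Section 5.2.1.4 repeats that bar.

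**The concern.** The re-treatment sentence is mandatory about the dose and makes no distinction between subjects who stayed at their allocated level and subjects who were reduced. A site that follows it literally returns a reduced subject to the level that led to the reduction, together with full-dose pembrolizumab. The main trigger for a delay, and so for a reduction, is a treatment-related event of Grade 3 or higher. Section 4.2.2.3 gives reason for care with the combination: 350 mg bid was well tolerated as monotherapy, but 3 of the 4 subjects given it with pembrolizumab had Grade 3 rash.

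A smaller gap goes with this. The text does not say whether reductions from the first course count toward the limit of two in the second.

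**Working it through.** The plan states no figure to reproduce. The check has two parts: whether the texts conflict, and how large the dose step would be.

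**Do the texts conflict?** Take a subject allocated 600 mg qd in Arm B who was reduced once, to 400 mg qd, before the CR stop.

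- Under Section 5.8.1.1, re-treatment starts at 600 mg qd.
- Under Section 5.2.2.1, the reduction to 400 mg qd is permanent and 600 mg qd is not allowed.

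Re-treatment is not clearly outside Section 5.2.2.1. Section 5.2.2 applies the modification guidelines at the start of each cycle without a carve-out, and Section 5.5.2 treats re-treatment for relapse after CR as part of the treatment phase.

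**Does anything else settle the dose?**

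- Investigator discretion in Section 5.8.1.1 covers whether to re-treat, not the dose.
- None of the four conditions concerns earlier reductions. Meeting the entry safety parameters describes current status, which a resolved toxicity need not block.
- The rechallenge note in Table 10 (Section 7.2.4) covers a serious, possibly drug-caused event, or re-exposure that carries significant additional risk: "THEN THE RECHALLENGE MUST BE APPROVED IN ADVANCE BY THE SPONSOR CLINICAL DIRECTOR AS PER DOSE MODIFICATION GUIDELINES IN THE PROTOCOL". It names no dose and covers only some reductions.
- Section 5.2.1.2 gives general flexibility to change doses on new data. It is not a rule for re-treating reduced subjects.

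**How large is the step?** Ratio = allocated dose ÷ dose after one or two level reductions, from Table 4. DL1 (350 mg bid) and the optional 10 mg and 30 mg doses are left out.

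| Arm and ladder | One reduction | Two reductions |
|---|---|---|
| B: 50, 100, 150, 200, 300, 400, 600, 900, 1200 mg qd | 2.0, 1.5, 1.33, 1.5, 1.33, 1.5, 1.5, 1.33 | 3.0, 2.0, 2.0, 2.0, 2.0, 2.25, 2.0 |
| C and D: 50, 100, 150, 200, 300, 400, 600 mg qd | 2.0, 1.5, 1.33, 1.5, 1.33, 1.5 | 3.0, 2.0, 2.0, 2.0, 2.0 |
| A (DL1A to DL6A): 100, 150, 200, 300, 400, 600 mg per day | 1.5, 1.33, 1.5, 1.33, 1.5 | 2.0, 2.0, 2.0, 2.0 |

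For the example subject, 600 ÷ 400 = 1.5 after one reduction. After two, 600 ÷ 300 = 2.0. The largest ratio is 150 ÷ 50 = 3.0.

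**How many subjects?** The documents give no rates. Assume, for illustration only, a CR rate of 1% to 5%, an earlier reduction in 25% to 50% of those, an elective stop in 50%, and progression with re-treatment in 30% to 50%.

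- Low: 182 × 0.01 × 0.25 × 0.5 × 0.3 = 0.07 subjects.
- High: 182 × 0.05 × 0.5 × 0.5 × 0.5 = 1.1 subjects.

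**The case against.** The strongest reply is that the protocol leans heavily one way. Permanence in Section 5.2.2.1 is unqualified, Sections 2.1 and 5.2.1.4 bar intrasubject escalation across the trial, and the Table 10 note sends the Sponsor back to the same modification guidelines. On that reading, the sentence in Section 5.8.1.1 only keeps the subject in the original cohort and was never meant to undo a reduction. That may well have been the intent. But the sentence specifies a dose as well as a Part, and it is the specific rule for re-treatment, so a site could reasonably follow it over a general one. Nothing in the text tells the site not to.

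It can also be said that a one-level reduction after a single resolved event does not prove intolerance of that MK-8353 dose, since causality is generally assigned to the combination (Section 7.2.4). That is fair as far as proof goes. Even so, Section 5.2.2.1 treats the event as sufficient reason never to return to the dose.

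Three points stand as limits. Very few subjects can be affected. The 3.0 ratio comes from a single rung (150 to 50 mg qd), and the other two-level ratios are 2.0 apart from one of 2.25. The natural reading of the two-reduction limit is already that earlier reductions count, so stating it is clarification only.

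**Conclusion.** The concern holds. For a subject reduced before the CR stop, Section 5.8.1.1 as written requires a re-escalation that Section 5.2.2.1 forbids, and no exception or order of precedence is given. The restart dose would be 1.33 to 2.0 times the last dose after one reduction and 2.0 to 3.0 times after two in Arms B, C and D, and 1.33 to 1.5 times and 2.0 times in Arm A. These ratios assume the planned Table 4 levels, and intermediate doses would make the steps smaller. The number of subjects affected is likely to be very small and could be zero. Section 5.8.1.1 excludes response and progression after re-treatment from ORR and PFS, so the issue is subject safety and internal consistency, not the efficacy estimates. It should be corrected.

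**What to change.** In Section 5.8.1.1, replace the dose wording so that re-treated subjects resume at *the MK-8353 dose being received when treatment was discontinued, that is, the initially allocated dose or, if it was reduced under Section 5.2.2.1, the reduced dose*. Add, as clarification, that reductions made before discontinuation count toward the two-reduction limit in Section 5.2.2.1.

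Nothing changes for subjects who were never reduced. The cost is one or two sentences at the next amendment, with no extra subjects, visits or data.
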